Primary objective: To assess time to first readmission within 30 days post-discharge from the hospital in patients recovering from acute myocardial infarction who use the mobile application as compared to a historical standard of care comparison group.

Secondary objectives: To assess medication adherence, patient satisfaction scores, app usability, patient activation, user engagement, user knowledge, and cost-effectiveness in patients recovering from acute myocardial infarction who use the mobile application. To assess recurrent myocardial infarction, ED visits, observation visits, and mortality in both groups.

3. **Background** (briefly describe pre-clinical and clinical data, current experience with procedures, drug or device, and any other relevant information to justify the research)

Nearly 20 percent of the 39 million patients discharged from the hospital in the US yearly are subsequently readmitted within 30 days with cardiac patients among the leading subset of patients with early readmissions. Current evidence raises major patient safety concerns with the discharge process and rate of avoidable morbidity and mortality. Furthermore, the cost to healthcare system is \$17.4 billion annually and accounted for 17 percent of total hospital payments from Medicare. Improving hospital discharge will likely reduce the rate of early hospital readmission which has been identified as a high priority for the US healthcare system to improve patient safety and reduce avoidable healthcare expenditures.

[name], MD, MHS, PI, has an extensive clinical research experience and experience in clinically testing mobile health technology, including a blinded, randomized mHealth Activity Trial (mActive), and evaluation of the Instant Blood Pressure mobile application. [name] leads the Cardiology mHealth Interest Group at Johns Hopkins which brings together multiple disciplines from

through the University. [name] also completed a HEXCITE Fellowship with Johns Hopkins Medicine and Technology Innovation Center focused on developing skills in designing, testing, and implementing mobile health projects with patients.

4. Study Procedures

Study design	A 1-month observational study, with a historical comparison group, involving Johns Hopkins Hospital and Johns Hopkins Bayview, as well as Massachusetts General Hospital, Reading Hospital, Franklin Square Hospital, and Union Memorial Hospital

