- v. After study completion, participants will participate in a phone interview, if they agree, to gather more information about their experience, using a standardized set of questions (see Supplemental Study Documents).
- w. Participants may be given the option to participate in future research studies.

Data collection for the Corrie Digital Health group and the historical standard of care comparison group to assess the primary outcome:

- a. Following study completion, we will submit requests to Johns Hopkins Hospital and Johns Hopkins Bayview Medical Center, Massachusetts General Hospital Partners group, and Reading Hospital administrative data managers to obtain the following data on both groups: age, sex, race, language, body mass index, marital status, smoking status, diagnosis of STEMI versus NSTEMI, insurance status (payor index), admission date, discharge date, type of intervention received in hospital (PCI or CABG), a discrete count of AHRQ identified Elixhauser comorbidities based on ICD-9-CM and ICD-10 diagnosis codes, discharge disposition, readmission, days to readmission, reason for readmission, ED visits, observation visits, and mortality.
- b. These variables will be obtained for both groups via the administrative databases to ensure standardization of variables and collection.
- c. For the historical control group we will query data for patients admitted to each hospital from October 1, 2015 to October 1, 2016 for a STEMI or NSTEMI. To obtain data for the Corrie Digital Health group, 30 days after the last enrolled participant is discharged from the hospital, we will send a list of

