Statistical plan including sample size justification and interim data analysis.	
Allowing for 10% of drop-outs during 30-day follow-up, the aim was to recruit N=200 in the intervention group and N=1,000 patients in the comparison group to provide around 90% power at the 2-sided 5% level of significance to detect a hazard ratio of 0.5 (ie, 50% reduction in a hazard of the intervention group), assuming 85% of patients in the comparison group survive or are not readmitted by the end of study (Stata stpower). The incident readmission rate of patients in our historical comparison group admitted to JHH and JHBMC was 16 cases per 100 person-months. We aim to detect a 50% risk reduction in readmission rates because our solution is comprehensive in nature and it is estimated that 76% of 30-day readmissions are potentially preventable using proven standards of care.
 
Our statistics will be primarily descriptive. We will examine characteristics of participants who join the study including demographics (e.g., age, sex, race/ethnicity, level of education, mHealth literacy, body mass index, marital status, occupation, annual income, insurance coverage) and clinical characteristics (e.g., severity of MI by TIMI/GRACE score, Killip Class, severity of cardiovascular disease by ejection fraction, medications, cardiac risk factor profile including dyslipidemia and lipid management characteristics as above), hypertension, diabetes, smoking, prior history of MI, and other comorbidities such as COPD, anxiety, and depression. We will examine primary and secondary outcomes as frequencies (percentage) for categorical variables and mean (SD) for continuous variables according to site of enrollment (JHH or JHBV) and type of mobile device (iPhone or Android). We will compare baseline characteristics of study participants using χ^2 and t-tests for categorical and continuous variables, as appropriate.
 
In assessing readmissions and cost-effectiveness, concurrent and historical controls will be matched to enrolled patients based on sociodemographic/clinical variables, and risk stratification using APR DRG / severity of illness scores (which are shown in the literature to be predictive for readmissions). We will conduct a Cox survival analysis to compare time to first readmission between the Corrie digital health group and the historical comparison group. We will build a Markov model of cost-effectiveness with the perspective of a hospital adopting Corrie technology, taking into account the lifelong outcome and cost of the Corrie discharge process versus the standard

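### The two-group data request and the matching and Cox plan name no hospital use before the index admission, although only the Corrie arm is filtered on smartphone ownership, impairment and illness severity

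*Combined protocol and SAP*

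**What the plan says.** Section 4 (data collection for the primary outcome, item a) lists what the administrative data managers will be asked for. The baseline part covers demographics, body mass index, smoking, payor, STEMI or NSTEMI, index dates, PCI or CABG, and "a discrete count of AHRQ identified Elixhauser comorbidities based on ICD-9-CM and ICD-10 diagnosis codes". The list ends with "discharge disposition, readmission, days to readmission, reason for readmission, ED visits, observation visits, and mortality". Item b adds: "These variables will be obtained for both groups via the administrative databases to ensure standardization of variables and collection".

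ED and observation visits carry no time window in item a. Section 2 makes them outcomes ("To assess recurrent myocardial infarction, ED visits, observation visits, and mortality in both groups"), and section 7 lists them as secondary outcomes.

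For the analysis, section 7 says that "concurrent and historical controls will be matched to enrolled patients based on sociodemographic/clinical variables, and risk stratification using APR DRG / severity of illness scores". It then states: "We will conduct a Cox survival analysis to compare time to first readmission between the Corrie digital health group and the historical comparison group". No Cox covariates are listed. The nearest history item in section 7 is in "hypertension, diabetes, smoking, prior history of MI, and other comorbidities such as COPD, anxiety, and depression", which describes participants who join the study and is not part of the two-group request.

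Section 4 also plans a separate extract, meant to assess selection bias, on 541 patients at the two Hopkins hospitals who were ineligible or declined. It takes readmission data and some covariates, and no prior hospital use.

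**The concern.** A patient's own recent hospital use bears directly on the tendency to be readmitted, and it is a hospital-use measure that the app cannot have affected. It could therefore serve both as an adjustment variable and as a pre-period check.

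It matters here because the filters fall on one arm. Under section 5, Corrie patients must own a smartphone (section 4 allows a loaned phone as resources permit), have no impairment that precludes use, and not be too ill to take part. Section 4 adds approval by the care team and consent. The historical group has none of these conditions. Each could plausibly remove frailer patients with more past admissions. If the other matching variables do not capture that difference, it lowers the Corrie readmission hazard whether or not the app works.

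**Working it through.** **1. Is prior use named anywhere?**

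| Place | Content | Pre-index hospital use |
|---|---|---|
| Section 4, item a (both groups) | demographics, index stay, Elixhauser count, outcomes | not named |
| Section 4, 541 non-enrolled (Hopkins) | covariates and readmission | not named |
| Section 7, matching | open-ended variables plus APR DRG / severity | not named |
| Section 7, Cox model | no covariates listed | not named |

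**2. The plan's own figure.** Section 7 gives 200 versus 1,000 patients, 10% drop-out, 85% event-free in the comparison group, HR 0.5 and around 90% power. After drop-out, 180 versus 900 remain. Events = 900 × 0.15 + 180 × (1 − 0.85^0.5) = 135.0 + 14.0 = 149.0. By Schoenfeld with allocation 1/6, z = √(149.0 × 1/6 × 5/6) × |ln 0.5| − 1.96 = 4.549 × 0.693 − 1.96 = 1.19, so power is 88.4%. The stated figure is reproduced, and this point does not alter it.

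**3. Illustration of the bias.** The documents give no prior-use figures, so all inputs here are assumptions. Let p_C and p_H be the shares of Corrie and historical patients with a prior admission, and h the readmission hazard ratio for such patients. With no app effect and nothing else adjusted:

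apparent HR = (1 + p_C(h − 1)) / (1 + p_H(h − 1))

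- p_C = 0.20, p_H = 0.30, h = 2: 1.20 / 1.30 = 0.923.
- p_C = 0.15, p_H = 0.35, h = 2.5: 1.225 / 1.525 = 0.803.
- Over h from 1.5 to 3, p_H of 30-40% and p_C of 10-20%: 0.96 to 0.67.

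**4. Effect on the test.** Events = 135 + 180 × (1 − 0.85^HR), and SE(ln HR) = 1/√(events × 5/36).

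- HR 0.923: about 160 events, SE 0.21, shift 0.080/0.212 = 0.38 SE. The two-sided 5% test rejects about 7% of the time.
- HR 0.803: about 157 events, SE 0.21, shift 0.219/0.214 = 1.02 SE. It rejects about 18% of the time.
- Over the wider grid: about 5.5% to 46%.

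**5. What a pre-period comparison could detect.** With 180 versus 900 patients, power to detect a difference in the share with a prior admission is about 80% for 20% versus 30%, and 26% for 25% versus 30%.

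**The case against.** Several parts of the case against this point stand, and they limit it.

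- **A reader might infer that adjustment for prior use is impossible under the plan.** The documents do not support that. Controls are to be "matched to enrolled patients based on sociodemographic/clinical variables", which is open-ended. APR DRG / severity scores are promised in section 7 although item a does not list them, so item a does not bound the matching set. What can be said is that prior use is named in neither place.
- **A reader might infer that selection is not examined at all.** It is. The extract on 541 non-enrolled patients can show whether those left out were readmitted more often, and section 7 also mentions concurrent controls. But the extract covers Hopkins only and uses post-discharge events. It cannot show whether the historical patients resembled the Corrie patients before the app.
- **The hazard ratios of 0.92 and 0.80 are crude.** Age, payor, Elixhauser count and severity may partly stand in for prior use, and any overlap moves the figures towards 1. The direction of imbalance is assumed too. The milder case barely changes the error rate, and nothing in the grid reaches the design HR of 0.5.
- **Availability is not documented.** The documents do not say that the databases reach back far enough, or that prior use is captured equally in the two calendar periods.
- **A pre-period ratio below 1 does not by itself show selection.** The comparator is historical, so changes in admission practice or recording could also move it. The check leaves prior use out of the matching, so it tests the other covariates rather than the final analysis. Its power for small differences is low.

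These points reduce the claim. They do not supply the missing variable.

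**Conclusion.** The point holds as a gap in the specification of the primary comparison. Hospital use before the index admission is not named in the two-group request, the matching or the Cox model, and the arms differ in entry filters that could plausibly be related to it. No planned check compares the historical and Corrie groups on pre-app hospital use.

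The size of any bias cannot be computed from the documents. The apparent HRs of 0.92 and 0.80 rest on assumed prevalences and hazard ratios, an assumed direction and no other adjustment. Residual bias after matching would probably be smaller. They show that such an imbalance could distort a null or modest effect. They do not show that the planned result is biased by that amount, or that the imbalance alone could produce an HR of 0.5. The plan should be changed, but the omission does not invalidate the study.

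**What to change.** 1. Confirm with the data managers that each database covers a 12-month look-back. For the earliest historical patients, admitted on October 1, 2015, this starts in October 2014.
2. Add to item a of the section 4 request, for both groups, counts of inpatient admissions, ED visits and observation stays in the 12 months before the index admission. Label them separately from the post-discharge outcomes.
3. Prespecify these counts in section 7 as matching variables, Cox covariates or both.
4. As a supporting check, report the prior-year admission rate ratio (Corrie/historical) with its confidence interval after matching on the other variables. State in advance that a ratio clearly below 1 signals non-comparability from selection or era, and that a ratio near 1 does not prove its absence.

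Cost: three more fields in a query that section 4 places after study completion, with no patient contact. Section 7 already quotes a historical readmission rate for the two Hopkins hospitals, so part of the historical data may have been drawn and could need a supplementary request. Limits: only use within each hospital's own system is likely to be visible, and capture may differ between the two calendar periods. Both should be reported with the result.

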	
participant identifiers to the hospital data managers.
 
d. In an ancillary study restricted to both groups of Hopkins participants, we will perform an Epic data extraction focused on measures of 2018 AHA/ACC guideline-directed cholesterol management such as serum lipid values upon admission through 12 months of hospital discharge, whether patients were on lipid lowering therapy at the time of admission, prescription of lipid lowering therapies at the time of discharge including statins and non-statins, whether the statin was a high intensity statin regimen at the time of hospital discharge, if patients were not on statin therapy due to a history of side effects, very high risk vs not very high risk status, and whether additional lipid lowering therapies were prescribed within 12 months of hospital discharge.
 
Data collection for patients who were deemed ineligible/declined to participate in the Corrie Digital Health group to assess selection bias:
 
a. Following study completion, we will submit requests to Johns Hopkins Hospital and Johns Hopkins Bayview Medical Center administrative data managers to obtain the following data on the 541 patient who were deemed ineligible/declined to participate in the Corrie intervention group: age, sex, race, marital status, smoking status, diagnosis of STEMI versus NSTEMI, insurance status (payor index), readmission, days to readmission, and reason for readmission.
 
b. These variables will be obtained via the administrative databases to ensure standardization of variables and collection to those who were enrolled in the Corrie intervention group.

--	--

MiCORE Reading Hospital cohort:

Reading Hospital is participating in this study through a grant from the Reading Hospital Foundation. The participation of patients recruited from Reading will be limited to the 30-day (approximate) initial enrollment period. The data collected from this cohort will be used to support the study’s primary outcome: 30-day readmission rate.

Study procedures for Reading Hospital	
Study design	Same as for primary cohort

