Study duration	Each participant will join the study for the entirety of their hospitalization following enrollment. This inpatient phase will last approximately 1 to 5 days, depending on the length of stay and the enrollment date, with the goal being to enroll the patient participant as early as possible in his/her hospitalization. Then enrollment will continue for 30 days following discharge for an approximate study duration of 30 to 40 days.
Routine care	Same as for primary cohort
Treatment failure or participant removal criteria	None (same as for primary cohort)
Participants receiving therapy when study ends or if a participant’s participation in the study ends prematurely	Same as for primary cohort
Procedural steps	Same as for the Corrie Digital Health group in the primary cohort, paragraphs a through n, and r through w. The Reading cohort will not participate in the procedural steps for the 6 and 12-month follow-ups, as described in paragraphs p and q.

	Data collection for the Corrie Digital Health group and the historical standard of care comparison group to assess the primary outcome will be the same.
--	--

5. Inclusion/Exclusion Criteria

a) The Corrie Digital Health group

Inclusion Criteria	Exclusion Criteria
-Patient admitted for acute myocardial infarction; MI present at the time of admission and Type I NSTEMI or STEMI -18 years or older - smartphone ownership	-Non-English speaking -Visual, hearing, or motor impairment which precludes use of the intervention -Persons not able to participate on due to severity of illness (e.g., intubated and on sedation in the setting of cardiogenic shock)

b) The Historical Comparison group

Inclusion Criteria	Exclusion Criteria
-Patient admitted for acute myocardial infarction; MI present at the time of admission and NSTEMI or STEMI -18 years or older	-Non-English speaking

6. Drugs/ Substances/ Devices

- a. The rationale for choosing the drug and dose or for choosing the device to be used.
- b. Justification and safety information if FDA approved drugs will be administered for non-FDA approved indications or if doses or routes of administration or participant populations are changed.
- c. Justification and safety information if non-FDA approved drugs without an IND will be administered.

Devices: Smartphone + Apple Watch + Silicone HealthBand + iHealth BP monitor +/- Apple TV

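### The selection-bias check on the 541 non-participants requests no mortality, disposition, discharge date, comorbidity or procedure data, so it cannot compare severity and can understate their readmission

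*Combined protocol and SAP*

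**What the plan says.** In Section 4 (Study Procedures), the step headed "Data collection for patients who were deemed ineligible/declined to participate in the Corrie Digital Health group to assess selection bias" covers "the 541 patient who were deemed ineligible/declined to participate in the Corrie intervention group". The request goes to two hospitals only: "we will submit requests to Johns Hopkins Hospital and Johns Hopkins Bayview Medical Center administrative data managers". Item a lists "age, sex, race, marital status, smoking status, diagnosis of STEMI versus NSTEMI", then "insurance status (payor index), readmission, days to readmission, and reason for readmission". Item b adds that these variables come from administrative databases, so that they match the enrolled group in definition and collection.

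For the Corrie and historical groups, item a of the data collection for the primary outcome (also Section 4) is longer. It includes both admission and discharge dates, PCI or CABG, and an Elixhauser comorbidity count, and it ends with "discharge disposition, readmission, days to readmission, reason for readmission, ED visits, observation visits, and mortality".

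Section 5 excludes from the Corrie group patients too ill to take part, giving as an example those "intubated and on sedation in the setting of cardiogenic shock". It also excludes non-English speakers and patients whose impairment prevents use of the app, and it requires smartphone ownership. Section 7 defines the primary outcome as time to first readmission in the 30 days after discharge.

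**The concern.** The primary comparison is non-randomised and uses historical controls. The historical group has no exclusion for severity of illness, impairment or lack of a smartphone, so selection into the Corrie group is a real threat, and part of it acts on how sick the patient is. The step on the 541 is the only one the plan labels as addressing this.

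Two things are missing. First, with no comorbidity count and no procedure, severity cannot be compared beyond STEMI versus NSTEMI and age. Second, with no death or disposition field, a patient who died in hospital, or who died after discharge without readmission, has the same record as one who was alive and readmission-free at day 30. Days to readmission does not help, because it exists only for those readmitted. If the sicker patients among the 541 die more often, their readmission proportion can look lower than it is, and the check can reassure when it should not.

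**Working it through.** **1. The two lists side by side.** The list for the Corrie and historical groups has 20 variables. The list for the 541 has 10, all of them among the 20. The ten absent are language, body mass index, admission date, discharge date, PCI/CABG, Elixhauser count, discharge disposition, ED visits, observation visits and mortality. Five of these bear on the check: mortality, disposition, discharge date, Elixhauser count and PCI/CABG.

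**2. The plan's own rate.** Section 7 gives 16 readmissions per 100 person-months for the Hopkins historical group and assumes 85% event-free in the comparison group. Under a constant hazard, exp(−0.16) = 0.852, so about 85.2% are event-free and 14.8% have the event at one month. The two figures agree. The 16% used below is a round assumption close to this. It is not a documented proportion for the 541.

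**3. Deaths in hospital.** Let r be readmission among those discharged alive, and d the share of the 541 who die before discharge. If these deaths stay in the denominator, the crude proportion is r × (1 − d).

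| d (assumed) | Deaths of 541 | Crude, r = 16% | Crude, r = 14.8% |
|---|---|---|---|
| 5% | 27 | 15.2% | 14.0% |
| 10% | 54 | 14.4% | 13.3% |
| 20% | 108 | 12.8% | 11.8% |

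The shortfall from 16% is 0.8, 1.6 or 3.2 percentage points.

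**4. Deaths after discharge without readmission.** These would remain even if the extract held only live discharges. Let q be their share of those discharged, and r = 16% among the rest.
- q = 2%: crude 0.16 × 0.98 = 15.7%; readmission or death 15.7% + 2% = 17.7%.
- q = 5%: crude 0.16 × 0.95 = 15.2%; readmission or death 15.2% + 5% = 20.2%.

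The requested fields give the first figure in each pair and cannot give the second.

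**5. How many deaths would hide a difference?** For a true rate r to look like 15%, the share dying without readmission must be 1 − 0.15/r:
- r = 16%: 6.3% (34 of 541)
- r = 18%: 16.7% (90 of 541)
- r = 20%: 25% (135 of 541)

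A small difference is easily hidden. Hiding a large one completely needs a high death share.

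**6. Scale against sampling error.** At 16% and n = 541, the standard error is √(0.16 × 0.84 / 541) = 1.6 points, and the 95% half-width is 3.1 points. The shifts in step 3 are therefore about half to two standard errors.

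**The case against.** Several points on the other side stand.

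- The plan fixes no denominator, estimator or handling of deaths for the 541. A reader might infer that the check as written does underestimate readmission. The documents support only that it can. The outcome runs from discharge, so an analyst might leave out in-hospital deaths, and the data managers might return only live discharges. Neither is stated, and post-discharge deaths would remain.
- The 541 include decliners and may include people without smartphones, who need not be sicker. No split is given, so no lower bound on the death share is justified.
- A reader might take item b as a promise of the full list that the short list then breaks. It concerns the source and definition of the variables listed, so there is no contradiction.
- A reader might infer that the 541 will be analysed as one pool, or that non-English speakers cannot be removed. The text names who is covered by the request, not how they are grouped, and screening records may hold language and the reason for non-participation. The plan does not say that they will be used.
- Age, sex, race, marital status, smoking, infarction type and insurance are requested, and they bear on who owns a smartphone or agrees to join. No harm is shown from leaving out body mass index, ED visits or observation visits.
- The check does not enter the Cox comparison, and Section 7 also plans matching on severity scores. That matching concerns controls, however, and does nothing for the 541. A comparison of readmission between enrolled and non-enrolled patients also mixes any app effect with selection, which makes baseline severity data more important to the check.

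**Conclusion.** The point holds as a limit on what the check can show. With the fields listed, it cannot compare comorbidity or procedure between enrolled and non-enrolled patients, and it cannot separate death without readmission from event-free survival. It can therefore understate readmission among non-participants.

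The size cannot be found from the documents. The crude proportion falls by the share who die without readmission: about 1 to 3 points for assumed in-hospital death shares of 5% to 20% and an assumed 16% among those discharged alive. These inputs are illustrations, and the calculation assumes that the deaths stay in the denominator.

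A reader might go further and conclude that the primary comparison is invalid or that its power is affected. The documents do not support that. Sample size, power and the Cox analysis do not depend on this list. What is at risk is an unjustified finding of no important selection.

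**What to change.** In item a of the request for the 541, add mortality with date of death, discharge disposition, discharge date, Elixhauser count and PCI/CABG. The full 20-variable list is not needed.

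Link each patient to the screening reason: eligible but declined, no smartphone, severity of illness or impairment, non-English, other.

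State the analysis:
- The denominator for 30-day readmission is patients discharged alive.
- Death before readmission is a competing event, or is reported in a readmission-or-death composite.
- Eligible decliners, who show volunteer bias, are reported separately from ineligible patients, who show the effect of the entry criteria.

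The cost is a longer field list on a request already planned to the same two hospitals, and an IRB amendment for additional data on people who did not take part. No patient contact is needed, and no sample size or power figure changes. The protocol words the request as still to be made.
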